RESEARCH STUDY PROTOCOL

Title:	OnCovid: natural history and outcomes of cancer patients during the COVID19 epidemic.
Protocol Version:	Version 3.0 dated 1st June 2020
Chief Investigator:	[name] [name]
Sponsor:	Imperial College London
IRAS Project ID:	282140

SYNOPSIS

Study title: OnCovid19: natural history and outcomes of cancer patients during the COVID19 epidemic.

Objectives: To describe the natural history and clinical outcomes of patients with cancer and Covid19 infection.

Study design & methodology: Retrospective observational study.

Research will be limited to secondary use of information previously collected in the course of normal care (without an intention to use it for research at the time of collection). Every aspect of this research will be undertaken by staff within a care team using information previously collected in the course of care for their own patients.

Routinely collected clinical data including patients' demographics, prior medical history, cancer history including prior and current anti-cancer therapy, co-morbidities will be collected in a data collection proforma. Results of routinely collected blood tests, radiologic assessment and therapies received by the patient will also be entered onto the database. Clinical outcomes including response to treatment and patients' survival will be evaluated in relationship to baseline clinico-pathologic profile.

Duration of Research: 2 years

Planned sample size:

Due to the descriptive and retrospective nature of this study, no sample size is required for hypothesis testing. We aim to describe clinical outcomes of consecutively presenting patients with a diagnosis of cancer and SARS-CoV-2 infection and aim to retrieve data on up to 5000 fulfilling eligibility criteria.

**Summary of
eligibility
criteria:** Inclusion criteria:

1. Be ≥ 18 years of age.
2. Have a confirmed diagnosis of malignancy of any type.
3. Have a confirmed diagnosis of SARS-CoV-2 infection.

**Number of study
centres:** 1

Endpoints: To retrospectively describe the survival of cancer patients affected by SARS-CoV-2 infection.

General Study Information

Name of sponsor: **Imperial College London**
Joint Research Compliance Office
[name]
Medical School Building
St Mary's Campus
[name]
[name]

Contact: [name]
Research Governance Manager
Email: [contact]
[contact]

Principal investigator: **[name] [name]**
Clinical Senior Lecturer and Consultant in Medical Oncology
Imperial College London

1.0 BACKGROUND AND RATIONALE

1.1 Introduction

Coronaviruses are a large family of viruses that are common in people and many different species of animals. Rarely, animal coronaviruses can infect people and then spread between people such as with MERS-CoV, SARS-CoV, and now with this new virus (named SARS-CoV-2).

The World Health Organisation (WHO) declared the coronavirus outbreak a pandemic on 11th March 2020, and it has now been officially recognised that the spread of COVID-19 is expected to affect most countries in the world.

The complete clinical picture with regards to COVID-19 is not fully known. Reported illnesses have ranged from very mild (including some with no reported symptoms) to severe, including illness resulting in death. While information so far suggests that most COVID-19 illness is mild, a report out of China suggests serious illness occurs in 16% of cases. Older people and people of all ages with severe chronic medical conditions — like heart disease, lung disease and diabetes, for example — seem to be at higher risk of developing serious COVID-19 illness. A CDC Morbidity & Mortality Weekly Report that looked at severity of disease among COVID-19 cases in the United States by age group found that 80% of deaths were among adults 65 years and older with the highest percentage of severe outcomes occurring in people 85 years and older.

The morbidity and mortality stemming from COVID-19 infection in cancer patients is not fully appreciated. Patients with cancer often have multiple co-morbid conditions and are often immune-suppressed as a result of their malignancy or systemic anti-cancer treatment.

2.0 STUDY OBJECTIVES

The overarching purpose of this retrospective, non-interventional study is to describe the features of COVID-19 infection in cancer patients, investigate its severity in this population and evaluate long-term outcomes by means of medical charts review of consecutive patients co-diagnosed with SARS-CoV-2 infection and malignancy.

3.0 STUDY DESIGN AND METHODS

3.1 Endpoints

1. Describe presenting characteristics and severity of SARS-CoV-2 infection in patients with cancer.
2. Evaluate prognostic factors for survival in patients with SARS-CoV-2 infection and cancer.

3.2 Methods

Patients with a diagnosis of malignancy and SARS-CoV-2 infection will be identified from electronic medical records and entered into a pre-designed database.

Methodologically, this project will be limited to secondary use of information previously collected in the course of normal care (without an intention to use it for research at the time of collection). Every aspect of this project will be undertaken by staff within a care team using information previously collected in the course of care for their own patients.

Routinely collected clinical information including patients' demographics, prior medical history, cancer history including prior and current anti-cancer therapy, co-morbidities will be collected in a data collection proforma. Results of routinely collected blood tests, radiologic assessments and therapies received by the patient will also be entered onto the database. Clinical outcomes including response to treatment and patients' survival will be evaluated in relationship to baseline clinico-pathologic profile. Clinico-pathologic will be correlated to patient's outcome, in particular overall survival (OS) as derived from electronic medical records.

The database consists of a Microsoft Excel spreadsheet including the following variables: age, gender, smoking status, prior comorbidities (cardiovascular, diabetes, dementia, pulmonary and kidney disease, liver disease, hypertension, immunosuppression), histotype of malignancy, date of first cancer diagnosis and stage of cancer at the time of SARS-CoV-2 infection, prior and current anti-cancer therapy, presenting symptoms at SARS-CoV-2 diagnosis and severity, routine blood tests at SARS-CoV-2 diagnosis (routine biochemistry, full blood count), radiologic data at diagnosis and follow up data (admission to intensive care, anti SARS-CoV-2-specific therapy, complications from SARS-CoV-2 infection).

Data collection will be completely solely by members of the patients' team. Resulting clinical data will be fully anonymised and stored in a password-protected NHS computer.

4.0 SUBJECT POPULATION

4.1 Subject number and selection

We plan to collect descriptive data in all consecutive patients with confirmed diagnosis of SARS-CoV-2 infection and cancer. Due to the descriptive and retrospective nature of this study, no sample size is required for hypothesis testing. We aim to describe clinical outcomes of consecutively presenting patients with a diagnosis of cancer and SARS-CoV-2 infection and aim to retrieve data on up to 5000 fulfilling eligibility criteria.

4.1.1 Inclusion criteria

The investigators will evaluate and include consecutive patients observed in the outpatients and inpatients facility of the study centre meeting all the following CRITERIA:

Inclusion criteria:

1. Be ≥ 18 years of age.
2. Have a confirmed diagnosis of malignancy of any type.
3. Have a confirmed diagnosis of SARS-CoV-2 infection.

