4.1.2 Exclusion criteria

Patients will not be entered in the study database when one or more of the following CRITERIA are present:

1. Unconfirmed diagnosis of SARS-CoV-2 infection
2. Insufficient clinical/follow up data.

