5.0 STATISTICAL ANALYSIS

5.1 Subject numbers.

5.1.1 Sample size.

For this observational, retrospective study, we propose a sample size of 5000 patients. Given the descriptive nature of this study no formal hypothesis testing is required. We will be retrospectively including patients fulfilling eligibility criteria between 1st January 2020 and 1st of April 2020.

5.2 Statistical methods.

Analysis of overall survival (OS) will validate the prognostic value of each clinico-pathologic trait collected at treatment initiation. Univariable analysis of survival will be used to derive median OS and associated 95% CI by using Kaplan-Meier methods and Log-rank tests.

The HRs and their associated CIs for OS will be computed using unadjusted and adjusted Cox proportional hazards models. We will employ a backward stepwise conditional model where each variable with an entry threshold of $p<0.05$ and an exit threshold of $p<0.10$ at each iteration. Proportional hazards will be adjusted for factors including active anticancer treatment type and features reflective of SARS-CoV-2 infection. Receiver-operating characteristics curve (ROC) will be used to test each variable for the accuracy of prediction of mortality at landmark survival endpoints (ie. 8, 12 weeks).

To test the predictive accuracy of each candidate prognostic variable we will use Harrell's rms packages to identify a subset of predictors by backward elimination, estimating the confidence intervals of the c-index statistics via bootstrapping (150 iterations).

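### Entry depends on being observed at the centre, not on where or when the infection was confirmed, and section 5.2 makes no allowance for late entry; if OS runs from SARS-CoV-2 diagnosis, mortality is understated and hazard ratios can be biased in either direction

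*Combined protocol and SAP*

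**What the plan says.** Section 4.1.1 will "include consecutive patients observed in the outpatients and inpatients facility of the study centre meeting all the following CRITERIA". The infection criterion reads only "Have a confirmed diagnosis of SARS-CoV-2 infection", with no place, no date and no maximum gap between confirmation and being seen.

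Section 3.2 describes how cases are found: "Patients with a diagnosis of malignancy and SARS-CoV-2 infection will be identified from electronic medical records and entered into a pre-designed database". The data are limited to what staff hold "using information previously collected in the course of care for their own patients". Its variable list names the date of first cancer diagnosis. It does not name the date or place of SARS-CoV-2 confirmation, or the date the patient was first observed at the centre.

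Section 5.1.1 sets the calendar limits: "We will be retrospectively including patients fulfilling eligibility criteria between 1st January 2020 and 1st of April 2020". It does not say which date must fall inside them. Section 4.1.2 excludes patients with "Insufficient clinical/follow up data" and gives no threshold.

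In section 5.2, "Univariable analysis of survival will be used to derive median OS and associated 95% CI by using Kaplan-Meier methods and Log-rank tests". Cox models and ROC curves at 8 and 12 weeks follow. Delayed entry is not mentioned and no OS start date is given. The only timing named there is in the sentence "Analysis of overall survival (OS) will validate the prognostic value of each clinico-pathologic trait collected at treatment initiation", whereas section 3.2 ties symptoms, severity and blood tests to SARS-CoV-2 diagnosis.

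**The concern.** Outpatients are expressly eligible. Someone whose infection was confirmed in the community or at another hospital, and who later attends clinic, therefore qualifies. A similar patient who died before attending may leave no record that the search would find. If survival is counted from confirmation, the first patient adds days at risk during which a death might not have been captured. This is left truncation. An analysis that puts every patient at risk from day 0 has too large a denominator early on, which is when infection deaths are likely to concentrate.

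Two results are at stake. One is the description of survival, the study's stated endpoint in the synopsis. The other is the evaluation of prognostic factors (section 3.1), where any covariate associated with late entry acquires a spurious HR. Active anticancer treatment is an obvious candidate, because it affects how often patients attend, and section 5.2 names treatment type as an adjustment factor. Enlarging the sample does not help: the bias stays and only the interval around it narrows.

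**Working it through.** The plan has no figure of its own to reproduce here. The 5000 in section 5.1.1 has no statistical inputs and is not in dispute. The documents give no mortality, share confirmed elsewhere or delay, so every input in steps 2 to 4 except the sample size is an assumption.

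**1. Does the calendar window remove the problem?** From 1 January to 1 April 2020 is 91 days. The landmarks are 56 and 84 days. If the window governs confirmation, it sets no short limit on the delay before first observation. If the patient must also be seen by 1 April, a 14-day delay requires confirmation by 18 March and a 42-day delay by 19 February. Long delays are then less common but still possible.

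**2. Effect on mortality and on a covariate with no true effect.** Let a share f be confirmed elsewhere and enter only if alive at delay D. The mortality observed when everyone is counted from day 0 is

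1 − S(84) / q, with q = (1 − f) + f × mean S(D).

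Assume S(84) = 0.70 with Weibull shape 0.8, so S(t) = exp[−0.357 × (t/84)^0.8]. Averaging over delays spread evenly, mean S(D) is 0.864 for 14-42 days and 0.954 for 0-14 days.

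- f = 0.35, 14-42 days: q = 0.65 + 0.35 × 0.864 = 0.952; mortality 1 − 0.70/0.952 = 26.5%; cumulative hazard 0.308.
- f = 0.10, 14-42 days: q = 0.986; mortality 29.0%; cumulative hazard 0.343.
- f = 0.15, 14-42 days: q = 0.980; mortality 28.5%; cumulative hazard 0.336.
- f = 0.05, 14-42 days: q = 0.993; mortality 29.5%.
- 0-14 days: mortality is 28.9% for f = 0.35 and 29.7% for f = 0.10.

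The cumulative-hazard ratios follow by division (for example 0.308/0.343 = 0.90). The Cox HRs come from simulating the same model.

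| Shares confirmed elsewhere, covariate present v absent | First seen (days) | Cumulative-hazard ratio | Cox HR, no delayed entry |
|---|---|---|---|
| 35% v 10% | 14-42 | 0.90 | about 0.89 |
| 15% v 10% | 14-42 | 0.98 | about 0.97 |
| 35% v 10% | 0-14 | 0.97 | about 0.97 |
| 10% v 35% | 14-42 | 1.11 | about 1.13 |
| equal, 5% or 10% | 14-42 | 1.00 | 1.00 |

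With start-stop entry at first observation, the Cox HR returns to about 1.00 in every row. Even with equal shares, 12-week mortality falls from 30% to 29.5% (5% confirmed elsewhere) or 29.0% (10%).

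**3. A second survival model.** Take S(t) = [c·exp(−t/m) + (1 − c)]·exp(−0.0005t) with c = 0.30, m = 10 days, f = 0.25 and D = 14 days. Then S(56) = 0.682 and S(14) = 0.769, so true 8-week mortality is 31.8%. The analysis without delayed entry gives 1 − 0.682/(0.75 + 0.25 × 0.769) = 27.6%. In simulation, ordinary Kaplan-Meier gave 27.7% and delayed-entry Kaplan-Meier 31.9%. Over c 0.2-0.4, m 10 or 20 days, f 0.10-0.50 and D 7-28 days, the shortfall runs from about 0.5 to 14 percentage points.

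**4. Against sampling error.** With 5000 patients, the 95% half-width for a mortality of 20-40% is 1.96 × √[p(1 − p)/5000], or 1.1 to 1.4 points. For the HR, 5000 × 27.8% = 1390 deaths in two equal groups (assumed) give a standard error of log HR of 2/√1390 = 0.054. A spurious HR of 0.89 then has z = 0.117/0.054 = 2.2, enough to pass the p<0.05 entry threshold in section 5.2. A spurious HR of 0.97 has z of about 0.6 and would not.

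**The case against.** The strongest reply has four parts.

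- **The design is a retrospective records search, not recruitment at a post-infection visit.** A patient already under the centre's care who was infected and died elsewhere could be found if the death reached the records. This stands. A reader might infer that patients who died first never enter, and the documents do not support that; they may be missed. Nor may confirmation have happened at any time, since section 5.1.1 sets a window.
- **Other text points to patients presenting with the infection.** Sections 2.0 and 4.1 speak of co-diagnosis and consecutive presentation. Late-seen patients may also lack baseline data and be excluded under section 4.1.2. This stands only in part. Neither section ties entry to the date of confirmation, and the exclusion could equally remove outside deaths with sparse records.
- **The OS origin is not stated.** If OS ran from first observation at the centre, there would be no immortal time. This stands, and the point is conditional on it. That origin would leave a selected group of survivors, with baseline data that predate time zero for late entrants.
- **The direction for treatment is not known.** A reader might infer that active treatment will look protective because treated patients attend more often. The same frequent attendance could mean they are more often tested at the centre, and reversing the shares moves the HR above 1. No passage settles this, and section 5.2 plans no efficacy claim for treatment.

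**Conclusion.** The concern holds in conditional form. The entry rule allows late entry, the planned methods ignore it, and no other section removes it. If OS runs from SARS-CoV-2 diagnosis and some patients were confirmed elsewhere and seen later, mortality is understated to the extent that deaths before first observation are missed. The HR of any covariate linked to late entry can be biased in either direction.

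The size cannot be known from the documents. Under the assumptions shown, a null HR ranges from about 0.89 to about 1.13 and is near 0.97 for small imbalances or short delays. With equal shares of 5-10% the HR is unaffected and 12-week mortality is 0.5-1 point too low. The effect could be negligible if few infections were confirmed elsewhere, but the variables listed in section 3.2 would not allow that to be checked. The change is worth making because it is cheap and the affected results are the study's main ones.

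**What to change.** - State in section 5.2 that OS runs from the date of SARS-CoV-2 confirmation, and in section 5.1.1 which date the calendar window governs.
- Add to the section 3.2 variable list the date and place of confirmation and the date first observed at the centre on or after confirmation.
- In the Kaplan-Meier, log-rank and Cox analyses, let patients confirmed elsewhere enter the risk set on that observation date (start-stop coding). Patients confirmed at the centre enter at day 0.
- Leave patients confirmed elsewhere who died with no later observation at the centre out of the delayed-entry analysis, and report their number. They never came under observation, and adding them only because the death was recorded would select on the outcome.
- Limit the 8- and 12-week ROC analyses and the c-index to infections confirmed at the centre.
- Report how many patients entered late.
- Add a sensitivity analysis restricted to infections confirmed at the centre. Delayed entry removes the bias only if the time of first observation is unrelated to prognosis given the covariates, and this comparison helps to judge that.

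The cost is one or two extra chart-review fields, start-stop coding, and slightly less early person-time and so slightly lower early precision.

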4.1.2 Exclusion criteria

Patients will not be entered in the study database when one or more of the following CRITERIA are present:

1. Unconfirmed diagnosis of SARS-CoV-2 infection
2. Insufficient clinical/follow up data.

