7.3 Confidentiality

A unique reference number will be used to anonymize the details of all participants. The investigator must ensure that the patient's privacy is maintained at all times. On the Case Report Form (CRF) or other documents, patients will be identified by a study ID number only. The investigator shall permit direct access to study source document for the purposes of monitoring, auditing, or inspection by the Sponsor, authorised representatives of the Sponsor and Regulatory Authorities.

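### Excluding patients for undefined insufficient follow-up selects on a post-infection condition at database entry; enter them, censor, and set data requirements per analysis

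*Combined protocol and SAP*

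**What the plan says.** Section 4.1.2 states: "Patients will not be entered in the study database when one or more of the following CRITERIA are present". The second criterion listed is "Insufficient clinical/follow up data". No minimum duration, list of variables or threshold is attached to it.

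The rule acts on the whole database, so it governs both endpoints in section 3.1. The first is to "Describe presenting characteristics and severity of SARS-CoV-2 infection in patients with cancer"; the second concerns prognostic factors for survival. Section 3.2 lists "presenting symptoms at SARS-CoV-2 diagnosis and severity" among the variables. It places intensive care admission, specific therapy and complications under follow-up data, and takes overall survival from electronic records.

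Section 5.2 plans the following: "Univariable analysis of survival will be used to derive median OS and associated 95% CI by using Kaplan-Meier methods and Log-rank tests". It adds Cox models, and ROC curves for mortality at 8 and 12 weeks. None of these is linked to the exclusion rule. The only log described is of database access (section 6.0). The text available for review asks for no count of excluded patients and no description of them.

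**The concern.** Whether follow-up is sufficient cannot be known when infection is diagnosed. Among patients whose record would stop early, those who die first have a complete outcome and stay in. Those alive when the record stops may be left out. Conditioning entry on this can distort the survival description even when the record stops for reasons unrelated to prognosis. If loss also differs between levels of a trait, it can distort that trait's hazard ratio in either direction.

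Because the rule acts at entry rather than at analysis, it also changes the group described under endpoint 1, where short follow-up is no reason to omit anyone. Without a count of exclusions, a reader of the results could not tell how much selection took place.

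**Working it through.** The plan gives no loss rate, mortality or definition on this point, so there is no figure to reproduce. The sample size of 5000 is stated without a calculation and plays no part here.

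**What each planned analysis needs**

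| Analysis | Follow-up needed |
|---|---|
| Presenting characteristics (endpoint 1) | None |
| Severity (endpoint 1) | None if graded at diagnosis, as the wording of section 3.2 suggests; some if graded by intensive care admission or complications. The grading is not defined. |
| Kaplan-Meier, log-rank, Cox | Any length; short follow-up is censored |
| ROC at 8 and 12 weeks | Known status at the landmark |

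Only the last row needs a minimum duration, and it does not require barring entry.

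**Mortality, 12-week reading.** All inputs are assumed. Half the patients are severe (50% die by 12 weeks) and half mild (10% die), so true mortality is 30%. Times to death are exponential, with weekly hazards −ln(0.5)/12 = 0.0578 and −ln(0.9)/12 = 0.00878. A random 25% would be lost at a time C, uniform over weeks 2 to 12.

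- Mean survival to C is (e^(−2λ) − e^(−12λ))/(10λ): 0.677 for severe, 0.941 for mild, average 0.809. The chance of dying before loss is therefore q = 0.191.
- Under exclusion, deaths kept = 0.75 × 0.30 + 0.25 × 0.191 = 0.2728.
- Patients kept = 0.75 + 0.25 × 0.191 = 0.7978.
- Exclusion gives 0.2728/0.7978 = **34.2%**. Censoring the same patients gives **30.0%** (simulation of 2,000,000 patients).

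**Other readings of insufficient, same loss**

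- Under 4 weeks: about 30.3% with exclusion, 30.0% with censoring (simulation).
- No follow-up at all: no difference, since such patients add nothing to a Kaplan-Meier curve either way.

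**Informative loss.** If instead 40% of mild cases are lost in weeks 2 to 12, exclusion gives 36.0% (12-week reading) and censoring 32.0%. The rule accounts for 36.0 − 32.0 = 4.0 points. The other 32.0 − 30.0 = 2.0 points remain under censoring.

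**Hazard ratio, true value 2.0.** Assume a trait in half the patients, overall 12-week mortality 30% (38.5% with the trait, 21.5% without; weekly hazards 0.0404 and 0.0202), loss in weeks 2 to 12 unrelated to outcome within each group, and the 12-week reading. For loss fraction p and hazard λ:

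- deaths D = (1−p)(1−e^(−12λ)) + p·E[1−e^(−λC)]
- person-weeks P = (1−p)(1−e^(−12λ))/λ + p·E[(1−e^(−λC)(1+λC))/λ]

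The rate ratio stands in for the Cox hazard ratio.

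| Loss with / without trait | D/P with trait | D/P without | Ratio |
|---|---|---|---|
| 10% / 20% | 0.3702/8.648 = 0.0428 | 0.1985/8.627 = 0.0230 | 1.86 |
| 20% / 10% | 0.3559/7.788 = 0.0457 | 0.2070/9.641 = 0.0215 | 2.13 |
| 5% / 40% | 0.3774/9.077 = 0.0416 | 0.1815/6.599 = 0.0275 | 1.51 |
| 40% / 5% | 0.3273/6.070 = 0.0539 | 0.2112/10.148 = 0.0208 | 2.59 |

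Censoring gives 2.0 in every row. Equal loss of 25% gives 1.98 under exclusion. On the 4-week reading, the 5%/40% rows become about 1.95 and 2.05.

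**Endpoint 1.** Suppose severity is recorded at diagnosis and 10%, 20% or 40% of mild cases have no follow-up and are excluded. The severe share moves from 50% to 0.5/0.95 = 53%, 0.5/0.90 = 56% or 0.5/0.80 = 62.5%.

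**The case against.** The rule has a purpose for one planned analysis. An ordinary ROC at 8 or 12 weeks cannot classify a patient censored earlier. That stands, but it supports a restriction within that analysis, not at entry.

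Heavy loss is not shown. Care teams abstract records of their own patients, who have cancer, so later records may well exist. The larger distortions need the 12-week reading, which the protocol does not state, and the extreme hazard ratios also need very unequal loss. This stands and limits any claim about size.

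Four stronger readings are tempting, and the documents do not support them.

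- *The rule contradicts the aim of taking all consecutive patients.* Section 4.1 qualifies that aim: "aim to retrieve data on up to 5000 fulfilling eligibility criteria".
- *The calendar forces short follow-up.* From the end of inclusion on 1 April 2020 to the protocol date of 1 June 2020 is 61 days, under 12 weeks. But no data cut-off is given and the study runs for 2 years, so follow-up need not stop there.
- *Excluded patients cannot be recovered.* Section 3.2 says "Patients with a diagnosis of malignancy and SARS-CoV-2 infection will be identified from electronic medical records" and section 7.3 says "The investigator shall permit direct access to study source document for the purposes of monitoring, auditing, or inspection". The exclusions could be reconstructed, so the missing count is mainly a reporting gap.
- *A small share of excluded survivors shows the harm done by the rule.* Excluding 5.8% of survivors and no deaths would move 30% mortality by one 95% confidence half-width at n = 5000 (1.3 points). Excluding 20% of deaths alone would give 0.24/0.94 = 25.5%. These compare with the truth, not with censoring. They measure total selection bias, part or all of which censoring might leave in place.

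**Conclusion.** The concern holds in a limited form. Criterion 2 is an undefined selection rule, applied at database entry, on something known only after infection. It is unnecessary for the Kaplan-Meier and Cox analyses and for presenting characteristics. For severity the same is true only if severity is graded at diagnosis.

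A reader might infer that the study's mortality will be overstated. The documents do not support that: bias can run either way, and if deaths and survivors are excluded equally, mortality is unbiased. Under the assumed inputs, the rule's own contribution to 12-week mortality runs from zero (no follow-up at all) through about 0.3 points (4-week reading) to about 4 points (12-week reading). A hazard ratio of 2.0 becomes 1.86 or 2.13 with moderately unequal loss and 1.51 or 2.59 with extreme loss, both on the 12-week reading. Every loss rate and mortality used is an assumption. That the answer depends so much on one undefined word is itself a reason to change it. The change should be made because it is cheap and the alternative is better, not because serious bias has been demonstrated.

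**What to change.** 1. Delete the follow-up part of criterion 2 and enter every patient who meets the three inclusion criteria.
2. Describe presenting characteristics in all of them, and severity wherever it is recorded.
3. Censor at the last date known alive in the Kaplan-Meier and Cox analyses.
4. For the 8- and 12-week ROC, use a time-dependent ROC that adjusts for censoring, or restrict that analysis to patients with known status at the landmark and give the number left out.
5. Replace insufficient clinical data with a stated minimum for each analysis. Patients who fall short stay in the database.
6. Report how many patients had no or short follow-up, with their baseline traits.
7. Optionally, add a Kaplan-Meier estimate stratified by recorded severity and weighted to the full cohort, stated to be valid only if loss depends on recorded severity alone.

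The cost is one reworded criterion, some extra abstraction and more missing cells in the tables. If the optional estimate is added, patients without recorded severity cannot enter it. Censoring does not remove informative loss, so item 6 is needed for readers to judge what remains.
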